6.0 Analysis Conventions

Definition of Induction Baseline

The Induction Baseline visit date is the date when the first dose of study drug is received and referred to as Day 1 or Week 0. If a subject has not taken any study drug during Induction Study, the randomization date will be used as Day 1. The Baseline value for a variable is defined as the last non-missing value on or before the date of the first dose of study drug.

Definition of Induction Final Observation

Final Observation in the 12-week double-blind Induction Study is defined as the last non-missing observation collected within 70 days following the last dose of study drug for

subjects who are not re-randomized nor enrolled in Study M14-347, and on or before the day of the first dose of study drug in the 44-week double-blind Maintenance Study for subjects who entered the Maintenance Study or the day of the first dose of study drug in Study M14-347 if the subjects are enrolled in Study M14-347. Of note, the efficacy, laboratory, and vital sign evaluations performed on the day of first dose of study drug in the double-blind Maintenance Study or Study M14-347 will be included in the efficacy and safety analyses for the Induction Study. AEs with onset on the date of the first dose of the Maintenance Study/M14-347 will be attributed to the Maintenance Study/M14-347.

Definition of Rx Days (Days Relative to the First Dose of Study Drug)

Rx Days are calculated for each time point of interest and it provides a quantitative measure of days between the event and the first dose date. That is, the Rx Day is calculated as the event date minus the date of first dose of study drug plus 1. The Rx Day will be a negative value when the time point of interest is prior to the date of first dose of study drug, and the Rx Day will be a positive value when the time point of interest is after the first dose date. By this calculation algorithm the first dose day is Rx Day 1, while the day prior to the date of first dose is defined as Rx Day -1 (there is no Rx Day 0). Rx Days are used to map actual study visits to the protocol specified study visits.

Dealing with Multiple Measurements Collected on the Same Day

For efficacy related analyses, if multiple measurements for a particular parameter are collected on the same day for the same subject, the average of those measurements will be used.

For safety related analyses, if multiple measurements are made for a particular laboratory or vital sign parameter on the same day for the same subjects, the later time one will be used if there is time or the average of the values will be used in the analyses of change from Baseline. For summaries and listings for shift from baseline and potentially significant values, all collected values within the pre-specified treatment window will be used.

Definition of Analysis Windows

Since subjects do not always adhere to the study visit schedule, the following rules will be applied to assign actual visits to protocol-specified visits including early termination visits. For each study visit mentioned in the protocol, a nominal or target day will be selected to represent the corresponding visit along with a window around the target day. Windows will be selected in a non-overlapping fashion so that a date collected on the CRF does not correspond to multiple visit windows. Moreover, windows will not discard any Post-Baseline measurement recorded on the CRF. If a subject had two or more actual visits in one visit window, the visit closest to the schedule visit will be used as the study visit for that window. If two visits are equidistant from the target, then the later visit will be used for reporting. If more than one assessment is collected on the same day, then the average of those assessments will be used in analyses.

Table 2. Visit Windows for Analysis of Efficacy Variables (Except IBDQ, EQ-5D, WPAI, and SES CD), hs-CRP, Urinalysis and Vital Signs for Induction Study

Scheduled Week	Nominal Day	Time Window (Rx Day Range)
Week 0	1 ^a	≤ 1
Week 2	15	2 – 22
Week 4	29	23 – 36
Week 6	43	37 – 50
Week 8	57	51 – 71
Week 12	85	72 – 98 ^b

Rx Day = date of visit – date of first study drug injection in double-blind induction study + 1

- a. Day of first dose of study drug in double-blind induction study. If a subject has not taken any study drug during Induction Study, the randomization date will be use as Day 1.
- b. Rx Day 98, or first dose of maintenance, or first dose of study drug in Study M14-347, whichever earlier.

Table 3. Visit Windows for Analysis of IBDQ, EQ-5D, and WPAI

Scheduled Week	Nominal Day	Time Window (Rx Day Range)
Week 0	1 ^a	≤ 1
Week 4	29	2 – 43
Week 8	57	44 – 71
Week 12	85	72 – 98 ^b

Rx Day = date of visit – date of first study drug injection in double-blind induction study + 1

- a. Day of first dose of study drug in double-blind induction study. If a subject has not taken any study drug during Induction Study, the randomization date will be use as Day 1.
- b. Rx Day 98, or first dose of maintenance, or first dose of study drug in Study M14-347, whichever earlier.

Table 4. Visit Windows for Analysis of Chemistry and Hematology for Induction Study

Scheduled Week	Nominal Day	Time Window (Rx Day Range)
Week 0	1 ^a	≤ 1
Week 2	15	2 - 22
Week 4	29	23 – 43
Week 8	57	44 – 71
Week 12	85	72 – 98 ^b

Rx Day = date of visit – date of first study drug injection in double-blind induction study + 1

- a. Day of first dose of study drug in double-blind induction study. If a subject has not taken any study drug during Induction Study, the randomization date will be use as Day 1.
- b. Rx Day 98, or first dose of maintenance, or first dose of study drug in Study M14-347, whichever earlier.

Table 5. Visit Windows for Analysis of SES-CD, Fistulas, and EIM for Induction Study

Scheduled Week	Nominal Day	Time Window (Rx Day Range)
Week 0	1 ^a	≤ 1
Week 12	85	2 – 168 ^b

Rx Day = date of visit – date of first study drug injection in double-blind induction study + 1

- a. Day of first dose of study drug in double-blind induction study. If a subject has not taken any study drug during Induction Study, the randomization date will be use as Day 1.
- b. Rx Day 168, or first dose of maintenance + 7 days, or first dose of study drug in Study M14-347 + 7 days, whichever earlier. No + 7 days for Fistulas and EIM.

Table 6. Visit Windows for Analysis of Fecal Calprotectin for Induction Study

Scheduled Week	Nominal Day	Time Window (Rx Day Range)
Week 0	1 ^a	≤ 1
Week 4	29	2 – 57
Week 12	85	58 – 112 ^b

Rx Day = date of visit – date of first study drug injection in double-blind induction study + 1

- a. Day of first dose of study drug in double-blind induction study. If a subject has not taken any study drug during Induction Study, the randomization date will be use as Day 1.
- b. Rx Day 112, or first dose of maintenance, or first dose of study drug in Study M14-347, whichever earlier.

CD-Related Concomitant Corticosteroid Therapy

Subjects in whom the CD-related corticosteroids (systemic or rectal corticosteroids) that were not being taken at Baseline and are initiated during the study or who have equivalent dose of these medications increased to greater than the dose taken at Baseline will be censored for efficacy assessments (i.e., will be considered non-responders for categorical endpoints and will have last non-missing values carried forward for non-categorical assessments) from that point through the end of the study. These subjects will continue to be evaluated in the safety population.

The equivalent steroid dose will be determined based on the table below:

Corticosteroid	Equivalent Dose (mg)
Cortisone	25
Hydrocortisone	20
Prednisone	5
Prednisolone	5
Triamcinolone	4.0
Methylprednisolone	4.0
Betamethasone	0.75
Dexamethasone	0.75
Budesonide	1
Beclomethasone	5
Beclometasone	5

Definition of Missing Data Imputation

The following imputation methods will be used to impute missing values in the efficacy analyses. In addition, an observed case analysis will be performed.

Non-Responder Imputation (NRI)

The NRI approach is used for binary efficacy variables. These variables can take values of 'Achieved' or 'Not Achieved' or may be missing for any reason including discontinuation from study. According to the NRI imputation approach, all missing values will be considered as 'Not Achieved.'

Last Observation Carried Forward (LOCF)

For all variables (categorical variables and continuous variables), the following rules will be used for the LOCF approach:

1. Baseline and Pre-Baseline values will not be used to impute the missing Post-Baseline values.

2. Missing values after Study Day 1 will be imputed using the latest non-missing values after Day 1 and prior to the missing value. If there are no non-missing values after Baseline, then the LOCF value will be missing.

Mixed-Effect Model Repeated Measure (MMRM)

The MMRM model will be used for continuous efficacy variables with longitudinal data as a sensitivity analysis. The MMRM model includes the baseline values as covariate; randomization strata, region (US versus non-US), treatment, time point and treatment-by-time point interaction as fixed effects; and subjects within treatment as random effect. An unstructured (co)variance structure will be used to model the within-subject error. The comparison at a time point will be the contrast between treatments at that time point.

Observed Case (OC)

Observed case analysis will be performed such that missing values will not be imputed. Subjects in whom the following CD-related systemic or rectal corticosteroids that were not being taken at Baseline and are initiated during the study or who have dosages of these medications increased to greater than the dose taken at Baseline will be censored for efficacy assessments (i.e., will be considered non-responders for categorical endpoints and the observed non-categorical assessments will be replaced by last non-missing values prior to censoring) from that point through the end of the study.

Imputation of Missing Dates

For Baseline, efficacy, and safety parameters, if the day and/or month are missing, the following conventions will be used to impute the missing dates:

- 01 for missing start day
- End of month for missing end day
- January 1st for missing start month
- December 31st for missing end month

Rule for CDAI Calculation

Up to 14 days of diary entries will be evaluated from the ePRO tool for the CDAI calculation for each visit. The diary entries on the days the subjects receive endoscopy preparation medications, the day of endoscopy procedure, and 2 days after endoscopy procedure will be excluded. For each CDAI subscore, the available scores from the most recent diary days (at least 4 days, up to 7 days) prior to actual day of the study visit will be summed, and then multiplied by the corresponding multiplier to get subtotal score. If available diary entries are fewer than 7 days, the subtotal score will be calculated as (summed total available score/number of days) \times 7 \times corresponding multiplier. The three subtotal scores that are based on ePRO (number of liquid/very soft stools, abdominal pain rating, and general well-being) will then be rounded to one decimal. The final CDAI is rounded to a whole number.

If a subject has less than 4 days of diary data, the total CDAI score will not be calculated and will be considered missing.

Sensitivity analyses will be performed to make use of all available data based on the above rule if more than 5% of subjects have less than 4 days of diary data.

Definition of Clinical Remission

CDAI < 150.

Definition of Clinical Response

Decrease in CDAI \geq 70 points from Baseline.

Definition of Enhanced Clinical Response

Decrease in CDAI \geq 100 points from Baseline.

Definition of Endoscopic Remission

Simplified Endoscopic Score for Crohn's Disease (SES-CD) ≤ 4 and at least 2 point reduction versus baseline and no subscore greater than 1 in any individual variable, as scored by central reviewer.

Definition of Endoscopic Response

Decrease in SES-CD $> 50\%$ from Baseline (or for a Baseline SES-CD of 4, at least a 2 point reduction from Baseline), as scored by central reviewer.

Stool Frequency + Abdominal Pain Score (SFPS)

SFPS is the CDAI components "Number of liquid or very soft stools" and "Abdominal pain" (Stool [liquid/soft] Frequency + Abdominal Pain Score). The sub-total score for each component is calculated as the sum of the 7 day diary score multiplied by the corresponding multiplier.

Definition of Time to Event (Clinical Remission, Clinical Response, or Hospitalization)

Time to event is defined as number of days from Study Day 1 to the date of first occurrence of an event. It is calculated as (date of first occurrence of Event – Study Day 1 date + 1). Subjects who discontinue prior to experiencing the event are censored at the time of discontinuation. Subjects who are not experiencing the event by Week 12 are censored at the Week 12 visit.

Definition of Symptomatic Remission

Average daily stool frequency ≤ 2.8 (and not worse than baseline) and average daily abdominal pain ≤ 1.0 (and not worse than baseline). The analysis will be only performed on subjects with baseline average daily stool frequency score ≥ 4.0 or average daily abdominal pain score ≥ 2.0 .

Definition of Symptomatic Response

Average daily stool frequency at least 30% reduction from baseline and average daily abdominal pain not worse than baseline or average daily abdominal pain at least 30% reduction from baseline and average daily stool frequency not worse than baseline. The analysis will be only performed on subjects with baseline average daily stool frequency score ≥ 4.0 or average daily abdominal pain score ≥ 2.0 .

Discontinued Corticosteroid Use at Each Visit during Induction Among Subjects Who Used Corticosteroids at Baseline

Discontinued steroid use at each visit is based on the steroid use on the date of CDAI measurement for that visit. If the subject has no CDAI for the visit, the date of vital signs will be used. If no vital signs date, then the steroid use on the nominal day for that visit will be evaluated.

If a subject discontinued the study, 'discontinued corticosteroid use' will be classified as No from that point through the end of the study.

If a subject met censoring criteria for CD-related concomitant therapy, 'discontinued steroid use' will be classified as No from that point through the end of the study.

SES-CD Scoring

All videotaped colonoscopies will undergo central review providing the investigator's SES-CD score meets the entry criteria. Two primary central reviewers will evaluate the videotaped colonoscopies separately and provide their SES-CD scores to Parexel. A third central reviewer will adjudicate between the two initial reviewers' SES-CD scores if there is discrepancy in any SES-CD variable. The adjudicator will select the final SES-CD score that he/she most agrees with from those provided by the two primary reviewers, and this final SES-CD score will be entered into the study database and be used for the study's efficacy analyses. If there is no discrepancy between the two primary central reviewers, that score will be entered into the study database and serve as the SES-CD score to be used for the study's efficacy analyses.

If there is a missing SES-CD individual variable in the SES-CD that serves as the SES-CD for the study's efficacy analyses, the following imputation rules will be applied:

The missing SES-CD individual variables at Baseline will be imputed as 0. The post-Baseline missing SES-CD individual variables will be imputed as 0 if there are 8 or fewer missing individual variables. If more than 8 individual variables are missing, the total SES-CD will be missing for that visit.

Bristol Stool Chart Score

Up to 14 days of diary entries will be evaluated from the ePRO tool for the Bristol Stool Chart calculation. These assessments on the day of endoscopy procedure, the day before endoscopy procedure (due to preparation medications), and 2 days after endoscopy procedure are excluded. The 7 most recent non-missing assessments will be used for the analysis. Bristol Stool Form Scale is not a continuous variable. The new variable Bristol Stool Chart score is defined as the number of days the subjects with Type 6 or Type 7 divided by the total number days with non-missing assessments, rounded to two decimal.

If a subject has less than 4 days of diary data, the Bristol Stool Chart score will not be calculated and will be considered missing.

If a subject achieved reduction from Baseline $\geq 50\%$, this subject will be classified as Bristol Stool Chart Responder.

Hs-CRP

From November 2014 to December 2015, Roche hs-CRP kit lot 604450 was in use at ICON. In December 2015 ICON altered the study team of a bias in the lot of the Roche Diagnostic C-creative protein high sensitive reagent. ICON then informed the study team of the extent of the under recovery in March 2016. This lot was "retrospectively expired" as the low standard beads agglutinated causing specimen results that are below 5 mg/L to be up to 25% lower than the accurate value. ICON later determined with Roche that the affected samples were those tested from May 18, 2015 to December 2015.

In the Study M14-115 approximately 423 samples were affected according to ICON. AbbVie obtained the final listing of affected samples/results from ICON on August 10, 2016. A correction factor developed by Roche and ICON will be applied to all affected specimens with a concentration between 0.51 to 4.99 mg/L and will replace the initially provided hs-CRP values in the study database.

For Study M14-115, both Roche and Abbott platform are used to measure hs-CRP. The study team has decided to use Abbott platform for CSR analysis. If hs-CRP was measured by Roche platform only, the value will be converted to Abbott equivalent by a conversion factor.

EuroQol-5D-5L (EQ-5D)

EQ-5D is a standardized measure of health status developed by the EuroQol Group in order to provide a simple, generic measure of health for clinical and economic appraisal. The EQ-5D consists of 2 pages. The first page measures 5 dimensions of the health status (mobility, self-care, usual activities, pain/discomfort, and anxiety/depression) with 5 levels per dimension (no problems, slight problems, moderate problems, severe problems, and unable corresponding to Level 1 to Level 5 respectively). The second page is an EQ Visual Analogue Scale (EQ VAS). EQ-5D health states, defined by the EQ-5D-5L descriptive system on the first page, may be converted into a single index value. The change from baseline of the index value and EQ VAS will be analyzed and reported. UK scoring algorithm will be used ([Table 7](#)).

Table 7. An EQ-5D-5L Value Set for England

	Central Estimate	Value for Health State 23245
Mobility		
No Problem	0	
Slight	0.051	0.051
Moderate	0.063	
Severe	0.212	
Unable	0.275	
Self-Care		
No Problem	0	
Slight	0.057	
Moderate	0.076	0.076
Severe	0.181	
Unable	0.217	
Usual Activities		
No Problem	0	
Slight	0.051	0.051
Moderate	0.067	
Severe	0.174	
Unable	0.190	
Pain/Discomfort		
No	0	
Slight	0.060	
Moderate	0.075	
Severe	0.276	0.276
Unable	0.341	
Anxiety/Depression		
Not	0	
Slight	0.079	
Moderate	0.104	
Severe	0.296	
Unable	0.301	0.301
The value for health state 23245:		$1 - 0.9675 \times (0.051 + 0.076$
$1 - 0.9675 \times (\text{sum of the subscores})$		$+ 0.051 + 0.276 + 0.301) = 0.270$

The index value is $1 - 0.9675 \times \text{sum of 5 components based on central estimates}$.

The minimum index value is -0.281 (health state 55555), and the maximum index value is 1 (health state 11111).¹

If one of the 5 dimensions is missing, the EQ-5D index value will be missing.

7.0 Demographics, Baseline Characteristics, Medical History, and Previous/Concomitant Medications

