**Statistical Methods:**

**Efficacy:**

The co-primary efficacy variables for the Induction Study are proportion of subjects with moderately to severely active CD that have achieved clinical remission, defined as CDAI < 150, at Week 4 and proportion of subjects with moderately to severely active CD that have achieved a decrease in SES-CD > 50% from Baseline (or for a Baseline SES-CD of 4, at least a 2 point reduction from Baseline), at Week 12. The comparison between treatment groups for the two co-primary efficacy variables will be performed using the Cochran-Mantel-Haenszel (CMH) test and will be stratified by hs-CRP at Baseline (< 10 and  $\geq$  10 mg/L) (the Screening hs-CRP will serve as the Baseline value), prior infliximab use, and Crohn's disease severity (CDAI  $\leq$  300, > 300) at Baseline. A CMH based two-sided 95% confidence interval for the difference between treatment groups will be calculated. The ITT set includes all subjects who were randomized at baseline. For the evaluation of co-primary endpoints, missing data of CDAI at Week 4 or missing SES-CD at Week 12 will be imputed using the non-responder imputation (NRI) approach. For Week 4 clinical remission, LOCF, OC and multiple imputation methods will be used as sensitivity analyses. For Week 12 endoscopic response (decrease in SES-CD > 50% from Baseline [or for a Baseline SES-CD of 4, at least a 2 point reduction from Baseline]), OC will be used as sensitivity analysis.

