#### **hs-CRP**

Blood samples for high-sensitivity C-Reactive Protein (hs-CRP) will be obtained per [Table 3](#). The Screening hs-CRP will serve as the Baseline value. The hs-CRP results in the Induction Study starting from Baseline to Week 8 will remain blinded to Investigator, study site personnel and the subject. The hs-CRP results in the Maintenance Study starting at Week 12 to Week 56 will be unblinded to the Investigator, study site personnel and the subject.

Blood draws should be performed after all efficacy assessments, questionnaires (CDAI, IBDQ, etc.), and vital sign determinations are obtained and before study drug administration during a visit.

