5.2 Variables Used for Stratification of Randomization

At Baseline, subjects will be randomized 3:2 to one of two double-blinded adalimumab Induction Study regimens (higher induction regimen or standard induction regimen). The randomization will be stratified by hs-CRP at Baseline (< 10 and ≥ 10 mg/L) using Screening hs-CRP values, prior infliximab use (Yes, No), Crohn's disease severity (CDAI ≤ 300 , > 300) at Baseline.

At Week 12, subjects will be re-randomized in a 1:1 ratio to one of two double-blinded exploratory treatment regimens (clinically adjusted [CA] regimen and adalimumab therapeutic drug monitoring [TDM] regimen). The re-randomization at Week 12 will be stratified by induction treatment regimen, clinical response (CR-70) status at Week 12, and decrease in SES-CD $> 50\%$ from Baseline per the site investigator reading at Week 12. Among subjects achieving decrease in SES-CD $> 50\%$ from Baseline at Week 12, the randomization will be further stratified by achievement of an SES-CD ≤ 4 and at least a 2 point reduction versus baseline and no subscore greater than 1 in any individual variable using the Week 12 SES-CD value provided by the site.

The randomization schedule will be prepared by the Statistics Department of AbbVie.

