10.2 Primary Efficacy Analyses

This section provides the details of the primary efficacy analysis for the Induction Study.

Co-Primary Efficacy Variables:

- Proportion of subjects who achieve clinical remission at Week 4 (CDAI < 150).
- Proportion of subjects with decrease in SES-CD > 50% from Baseline (or for a Baseline SES-CD of 4, at least a 2 point reduction from Baseline) at Week 12.

Analysis Data Set for the Primary Efficacy Analysis:

The primary efficacy analysis will use the ITT analysis data set.

Imputation Method Used for the Primary Efficacy Analysis:

Missing CDAI at Week 4 or SES-CD at Week 12 will be imputed using the non-responder imputation (NRI) approach.

Statistical Method of the Primary Efficacy Analysis:

The comparisons between treatment groups on the two co-primary efficacy variables will be performed using the Cochran-Mantel-Haenszel (CMH) adjusted for hs-CRP at Baseline (< 10 and ≥ 10 mg/L), prior infliximab use (or prior anti-TNF use for subjects randomized under original protocol), and Crohn's disease severity (CDAI ≤ 300 , > 300) at Baseline. A CMH based two-sided 95% confidence interval for the difference between treatment groups will be calculated. Breslow-Day test for homogeneity of odds ratios will be performed as well. An exact CMH test will be used to handle zero cells.

For Week 4 clinical remission (CDAI < 150), LOCF, OC and multiple imputation methods will be used as sensitivity analyses. For Week 12 endoscopic response, OC will be used as sensitivity analysis.

In addition, as sensitivity analyses, the logistic regression including treatment, the randomization stratification factors and additional clinically important factors such as corticosteroid use at Baseline, IMM use at Baseline, Baseline fecal calprotectin, Baseline SES-CD, and Region (US versus ex-US) will also be performed for the co-primary endpoints.

The co-primary endpoints will be tested prior to the ranked secondary endpoints.

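### The Induction SAP's Baseline rule has no hs-CRP exception, so the hs-CRP stratum in the co-primary and ranked secondary analyses is specified inconsistently with the protocol and the randomisation

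*SAP*

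**What the plan says.** **Protocol.** Section 5.3.1.1 (hs-CRP) states: "The Screening hs-CRP will serve as the Baseline value". The synopsis, under Statistical Methods, repeats this specifically for the co-primary CMH test: "the Screening hs-CRP will serve as the Baseline value". Section 8.3 stratifies the randomisation on the Screening result.

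**Induction SAP, randomisation.** Section 5.2 describes the factor as Baseline hs-CRP cut at 10 mg/L, "using Screening hs-CRP values, prior infliximab use (Yes, No".

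**Induction SAP, analysis.** Section 6.0 defines the Baseline value of any variable as "defined as the last non-missing value on or before the date of the first dose of study drug". Table 2 in the same section names hs-CRP, sets Week 0 at nominal Day 1 with a window of Day 1 or earlier, and keeps the visit nearest the target day. Section 10.2 compares the arms "using the Cochran-Mantel-Haenszel (CMH) adjusted for hs-CRP at Baseline", with the same cut, plus prior infliximab use and CDAI severity. "A CMH based two-sided 95% confidence interval for the difference between treatment groups will be calculated". Section 10.3 uses the same factors for the ranked secondaries. None of these passages says that the Screening hs-CRP is meant.

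**Platform.** Section 6.0 also states: "If hs-CRP was measured by Roche platform only, the value will be converted to Abbott equivalent by a conversion factor".

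**Declared differences.** Section 12.1 lists no change from the protocol.

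**The concern.** A programmer who follows Sections 6.0 and 10.2 in order would build the hs-CRP stratum from the Baseline-visit sample. One who follows the protocol, or Section 5.2, would build it from the Screening sample. These are different blood draws, so a subject near 10 mg/L can fall in different strata, and the two routes then give different p-values for the same data.

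The SAP carries a Screening-as-Baseline statement for CDAI and for SFPS in its schedule notes and design section. Its absence for hs-CRP could therefore be taken as deliberate.

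The choice feeds both co-primary tests and all 15 ranked secondaries. Under Section 10.4 both co-primaries must reach 0.05, and ranked testing stops at the first failure, so a borderline result could turn on an unstated choice. The same gap affects the hs-CRP subgroups in Section 10.5 and the change-in-hs-CRP endpoint, where protocol and SAP would start from different Baseline values.

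**Working it through.** **1. Are there two samples?** Yes. The schedule has hs-CRP at both Screening and Baseline. Protocol 5.3.1.1 confirms that Baseline results exist: "The hs-CRP results in the Induction Study starting from Baseline to Week 8 will remain blinded". The 14-day waiver of repeat tests in the protocol's Clinical Laboratory Tests text covers chemistry, haematology and urinalysis, not hs-CRP. For a subject with no Baseline-visit result the two rules agree.

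**2. Which sample does each text select?**

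| Text | hs-CRP sample |
|---|---|
| Protocol 5.3.1.1 and synopsis (co-primary CMH) | Screening |
| Protocol 8.3, SAP 4.2 and 5.2 (randomisation) | Screening |
| SAP 6.0, Baseline definition | Last before or on first dose: Baseline visit |
| SAP 6.0, Table 2 | Nearest Day 1: Baseline visit |
| SAP 10.2 and 10.3, CMH and ANCOVA | Not named |
| SAP 10.2, logistic sensitivity model | Randomisation factors |

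The other two factors are not in doubt. Screening CDAI is the Baseline CDAI (SAP Table 1, note a), and prior infliximab use does not depend on a visit value.

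**3. The plan's own power.** Inputs from SAP 4.3: 300 v 200, Fisher's exact test, two-sided 0.05. Power is the sum of Bin(x1; 300, p1) × Bin(x2; 200, p2) over all tables with Fisher p ≤ 0.05.
- Week 4 remission, 50% v 30%: 0.9939 (stated 99%).
- Week 12 endoscopic response, 66% v 44%: 0.9978 (stated about 99%).
- Joint, lower bound: 0.9939 + 0.9978 − 1 = 0.9917 (stated above 98%).

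The stated figures reproduce. They come from an unstratified test, so the choice of hs-CRP visit does not enter them.

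**4. What switching the hs-CRP sample does to the CMH test.** Simulation of 500 subjects, randomised 3:2 in blocks of five within the eight Screening strata, at the planned Week 4 rates (50% v 30%) and under the null (40% in both arms). Assumptions not in the documents: half the subjects at or above 10 mg/L, 25% with prior infliximab (the enrolment cap), half with CDAI above 300, and 5%, 10% or 20% crossing 10 mg/L between visits (25, 50 or 100 subjects). The odds ratio of outcome for high hs-CRP is 0.5 or 0.33, driven by either visit's value; the other two factors have no effect on outcome. For stratum k with n subjects (n1 higher, n0 standard), t responders and a responders on the higher regimen:

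CMH = [Σ(a − n1·t/n)]² / Σ[n1·n0·t·(n − t) / (n²(n − 1))], rejecting above 3.841.

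There were 2,500 trials per cell. Each trial was analysed both ways, shown as Screening / Baseline-visit strata:

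| Outcome driven by | Odds ratio | Crossing | Power | Type I error |
|---|---|---|---|---|
| Baseline | 0.5 | 5% | 0.9948 / 0.9948 | 0.0512 / 0.0504 |
| Baseline | 0.5 | 10% | 0.9936 / 0.9940 | 0.0516 / 0.0532 |
| Baseline | 0.5 | 20% | 0.9932 / 0.9940 | 0.0488 / 0.0504 |
| Baseline | 0.33 | 5% | 0.9960 / 0.9976 | 0.0576 / 0.0580 |
| Baseline | 0.33 | 10% | 0.9948 / 0.9956 | 0.0492 / 0.0472 |
| Baseline | 0.33 | 20% | 0.9964 / 0.9960 | 0.0448 / 0.0452 |
| Screening | 0.5 | 5% | 0.9976 / 0.9976 | 0.0440 / 0.0444 |
| Screening | 0.5 | 10% | 0.9940 / 0.9936 | 0.0508 / 0.0512 |
| Screening | 0.5 | 20% | 0.9968 / 0.9964 | 0.0484 / 0.0488 |
| Screening | 0.33 | 5% | 0.9968 / 0.9960 | 0.0516 / 0.0508 |
| Screening | 0.33 | 10% | 0.9984 / 0.9972 | 0.0512 / 0.0476 |
| Screening | 0.33 | 20% | 0.9968 / 0.9952 | 0.0556 / 0.0548 |

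The largest power change is 0.16 points (for example 0.9968 − 0.9952) and the largest type I change is 0.36 points (0.0512 − 0.0476). The Monte Carlo standard error of a type I rate is √(0.05 × 0.95 / 2500) = 0.0044. The mean estimated difference is 0.20 under both.

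**5. Platform.** The reagent-lot correction applies to readings of 0.51 to 4.99 mg/L that were up to 25% low. The highest corrected value is about 4.99 / 0.75 = 6.65 mg/L, below the cut. The Roche-to-Abbott conversion could move a value across 10 mg/L, but no factor is given and neither is the platform used at randomisation, so this cannot be sized.

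**The case against.** The strongest reply is that the specific text points to Screening. Section 5.2 attaches the same label and cut to Screening values, and Section 10.2 reuses them. The infliximab factor in Section 10.2 switches to prior anti-TNF use for subjects randomised under the initial protocol, which makes sense only if the factors follow the randomisation. The synopsis names the Screening value for this very test, and Section 12.1 declares no departure.

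Most of this stands. It shows that Screening was probably intended. It does not make the SAP say so: Section 5.2 describes how subjects were randomised, while Section 6.0 defines analysis values. Within Section 10.2 the logistic model invokes the randomisation factors and the CMH does not.

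Two stronger readings are tempting, and the documents support neither.
- A reader might infer that the co-primary analysis abandons the randomised strata. The SAP never says that. At most one of three factors is in question, and only for subjects who cross 10 mg/L.
- A reader might infer a material power loss in the ranked secondaries. Simulations at about 72% to 79% power, with assumed visit correlations of 0.7 to 0.9, lose 0.2 to 2.8 points (the worst case is 72.4% to 69.6%). Those correlations and effect sizes are assumptions; the documents give no effect size for any ranked secondary.

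**Conclusion.** The inconsistency is real. The protocol sets one Baseline hs-CRP value, the SAP's general rule and its Table 2 select another, and the SAP's analysis sections do not say which governs. Both values are pre-treatment, so the test is valid and the estimate unbiased under either reading. At the planned Week 4 rates the effect on power is below 0.2 points, given the assumed 5% to 20% reclassification and the assumed odds ratios. No stated figure changes.

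The gain from settling it is a single pre-specified analysis that matches the randomisation and the protocol. Low severity; a free improvement.

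**What to change.** - **SAP 10.2 and 10.3:** state that the CMH and ANCOVA factors are the stratification categories recorded at randomisation, as the logistic sensitivity model already has it. For hs-CRP, specify the Screening result as used at randomisation, not the platform-converted value.
- **SAP 6.0:** add that Screening hs-CRP is the Baseline value, and make the Week 0 row of Table 2 agree. This settles the subgroups and the change endpoint; the platform rule can continue to apply to the change endpoint.
- **Maintenance SAP 6.0:** it repeats the same Induction Baseline definition and analyses change in hs-CRP from it, so the same sentence belongs there.

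The cost is wording only, since the randomisation categories already exist. It should be in place before the Week 12 database cut, because SAP 4.4 treats an analysis at that cut as the sole co-primary analysis.
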